## LIST OF ABBREVIATIONS

AE	adverse event
CFR	Code of Federal Regulations
CRF	case report form
DMC	Data Monitoring Committee
DSMB	Data Safety Monitoring Board
FDA	Food and Drug Administration
GCP	Good Clinical Practice
HIPAA	Health Insurance Portability and Accountability Act of 1996
ICF	informed consent form
ICH	International Conference on Harmonisation
IEC	Independent Ethics Committee
IRB	Institutional Review Board
IV	intravenous
mEq	milliequivalent
PI	Principal Investigator
SAE	serious adverse experience

## PROTOCOL SYNOPSIS

TITLE	Cryoanalgesia vs. Thoracic Epidural for Post-operative Pain Control following the Nuss Procedure
SPONSOR	UCSF Department of Surgery, Division of Pediatric Surgery
NUMBER OF SITES	1: UCSF Benioff Children's Hospital
RATIONALE	
Pectus excavatum is the most common congenital chest wall deformity, affecting approximately 1 out of every 1000 live births. It presents as a depression of the anterior chest wall, which can compress the heart and lungs, causing symptoms such as shortness of breath, exercise intolerance, and chest pain. The minimally invasive pectus excavatum repair, known as the Nuss procedure, is a common corrective procedure. It uses an implanted, thoracoscopically-guided convex metal bar to immediately reshape the chest wall. The benefits of this method compared to open repair include smaller incisions, no cartilage resection or osteotomy, and reduced operative times. However, the immediate reshaping of the chest wall results in significant post-operative pain, which can be challenging for patients, families, and clinicians. The ability to adequately control this post-operative pain is the primary determining factor for length of hospitalization following the procedure.
 
There is no standardized protocol for the management of pain following the Nuss procedure. Epidural analgesia and patient controlled analgesia (PCA) are the two most commonly used techniques, employed either independently or together. While epidural analgesia has been shown to be more effective than PCA alone for the first few postoperative days, it carries significant risks and is limited to the first two to three post-operative days, at which time patients must be transitioned to alternate methods. Cryoanalgesia is a means of long-term local nerve blockade, which has previously been used in adults for acute pain control following thoracotomy, as well as for treatment of chronic thoracic pain due to surgery or post-herpetic neuralgia. Anecdotally, cryoanalgesia has been effective at controlling acute post-operative pain following the Nuss procedure. The procedure is particularly well-suited to the application of cryoanalgesia, as the operative exposure directly visualizes the intercostal nerves. However, no randomized trials have been performed to more rigorously evaluate this treatment. We therefore propose a randomized, prospective trial to evaluate cryoanalgesia compared to epidural analgesia for the Nuss procedure.

STUDY DESIGN	This study is a prospective, randomized trial to compare cryoanalgesia to standard epidural analgesia for post-operative pain management in patients undergoing minimally invasive pectus excavatum repair (the Nuss procedure). 20 subjects will be randomized in 1:1 ratio to receive cryoanalgesia or epidural analgesia prior to their procedure.
PRIMARY OBJECTIVE	To compare post-operative length of stay in patients receiving cryoanalgesia vs. thoracic epidural analgesia for the Nuss procedure

SECONDARY OBJECTIVES	To compare post-operative pain scores, pain medication usage, side effects, and total cost of hospital stay in patients receiving cryoanalgesia vs. thoracic epidural analgesia for the Nuss procedure
NUMBER OF SUBJECTS	20
SUBJECT SELECTION CRITERIA	
Inclusion Criteria: Otherwise healthy male or female patients with pectus excavatum deformity, scheduled for Nuss procedure for chest wall correction, at least 13 years of age at time of Nuss procedure.
 
Exclusion Criteria:
 
 
• Age less than 13 years at time of surgery
 
• Pre-op pain medication usage
 
• Pectus carinatum
 
• Poland's syndrome or other complex chest wall anomaly
 
• Previous repair of Pectus Excavatum by any technique
 
• Previous thoracic surgery
 
• Congenital heart disease
 
• Bleeding dyscrasias
 
• History of previous problems with anesthesia or major anesthetic risk factors
 
• Pregnancy
 
• Non-English speaker
 

TEST PRODUCT, DOSE, AND ROUTE OF ADMINISTRATION	
AtriCure cryosurgical system (AtriCure, Inc., West Chester, Ohio)
 
The cryoprobe will be applied to the intercostal nerve under thoracoscopic visualization at the level of the incision and 2 interspaces above and below, bilaterally. The temperature and duration of cryoablation therapy is pre-set by the probe and cryosurgical system at 2 minutes to -60°C. Each nerve will receive one cycle of cryoablation.

CONTROL PRODUCT, DOSE AND ROUTE OF ADMINISTRATION	
Thoracic epidural catheter will be placed by the pediatric anesthesia team prior to Nuss procedure. Catheters will be placed using sterile technique at approximately T5-6 or T6-7 interspaces; procedure specifics are dependent on the attending anesthesiologist's patient-dependent preference. Whether the patient will be awake or asleep for epidural placement will be at the discretion of the attending anesthesiologist. After placement, epidural infusion will begin with 0.1% ropivacaine and 2mcg/cc fentanyl. No bolus doses will be used.

DURATION OF SUBJECT PARTICIPATION AND DURATION OF STUDY	Subjects will be on study for 1 year  Screening: 1 week (prior to initial consultation) Treatment: 3-7 days (subjects to be admitted to the hospital) Follow-up: 1 year  The total duration of the study is expected to be 1.5 years. 6 months for subject recruitment and 1 year following final recruitment for subject follow-up.
CONCOMITANT MEDICATIONS	Allowed: all deemed necessary by primary team or pediatric pain service  Prohibited: none
EFFICACY EVALUATIONS	
PRIMARY ENDPOINT	
 
Post-operative hospital length of stay
 

SECONDARY ENDPOINTS	
 
Post-operative pain scores
 
Pain medication usage
 
Side effects
 
Total hospitalization cost
 

SAFETY EVALUATIONS	Incidence of adverse events
PLANNED INTERIM ANALYSES	Serious adverse events will be monitored by the committee on an ongoing basis throughout the study.
STATISTICS Primary Analysis Plan	Patient baseline characteristics will be analyzed with descriptive statistics (ie. mean age, % male, mean pectus severity index, etc.). Our primary outcome will be post-operative length of stay, which will be analyzed using a two-tailed unpaired t test, with results considered statistically significant for $p < 0.05$ . Secondary outcomes include post-operative pain scores, pain medication usage, and side effects. Pain scores will be analyzed with Mann-Whitney rank sum tests (to compare between groups at each time point) and Wilcoxon signed-rank test (to compare scores within groups over time), with results considered statistically significant for $p < 0.05$ . Pain medication usage between the two groups will be analyzed with two-tailed unpaired t test, again with results considered statistically significant for $p < 0.05$ . Given our small sample size and the low rate of complications with both analgesic methods, we expect very limited side effect data. A descriptive overall side effect rate will be calculated for each arm of the study, and the individual side effects will be listed in a table. A cost analysis will be performed, comparing the total cost of hospitalization between the cryoanalgesia and epidural groups. Difference in total cost will be assessed with two-tailed unpaired t test.

Rationale for Number of Subjects	
We used the UCSF Clinical & Translational Science Institute web-based sample size calculator (http://www.sample-size.net/sample-size-means/) to determine study size. Based on previous Nuss procedures over the past 2 years at our institution, we determined the mean length of hospitalization was 7 days, with a standard deviation of 1.3 days. From anecdotal data from our prior experience, as well as from speaking with other surgeons utilizing cryoablation, we expect patients in the cryoanalgesia group to have approximately 2 days shorter hospital stay. With type I error rate of 0.05 and type II error rate of 0.1 (yielding 90% power), our study would need 18 patients total. Allowing for some dropout, we will plan to enroll 20 patients to the study.

---	---

## 1 BACKGROUND

Pectus excavatum is the most common congenital chest wall deformity, affecting approximately 1 out of every 1000 live births. It presents as a depression of the anterior chest wall, which can compress the heart and lungs, causing symptoms such as shortness of breath, exercise intolerance, and chest pain. The minimally invasive pectus excavatum repair, known as the Nuss procedure, is a common corrective procedure. It uses an implanted, thoracoscopically-guided convex metal bar to immediately reshape the chest wall. The benefits of this method compared to open repair include smaller incisions, no cartilage resection or osteotomy, and reduced operative times. However, the immediate reshaping of the chest wall results in significant post-operative pain, which can be challenging for patients, families, and clinicians. The ability to adequately control this post-operative pain is the primary determining factor for length of hospitalization following the procedure.

There is no standardized protocol for the management of pain following the Nuss procedure. Epidural analgesia and patient controlled analgesia (PCA) are the two most commonly used techniques, employed either independently or together. Thoracic epidural analgesia has been shown, with limited data, to be more effective than PCA alone for the first few postoperative days, but carries significant risks, including nerve damage, infection, and respiratory depression. Epidural analgesia also reduces post-operative mobility, and often necessitates the use of urinary catheters, which can increase risk of urinary tract infections. The use of epidural analgesia is limited to the first two to three post-operative days, at which time patients must be transitioned to alternate methods. This may increase length of stay, as it introduces an intermediate step prior to home oral regimen.

Thus, there is significant room for improvement in post-operative pain management in the Nuss procedure. One possible solution is the addition of a local nerve block with cryoanalgesia. The use of cold to numb pain is one of the oldest forms of analgesia, dating back at least to Hippocrates (460-377 BC), who described the use of ice and snow packs for relieving surgical pain. Today, the term “cryoanalgesia” refers to the localized freezing of peripheral nerves. Freezing occurs through application of a “cryoprobe,” which releases high-pressure carbon dioxide or nitrous oxide that rapidly expands, causing cooling via the Joule-Thomson effect to temperatures of -50 to -70 °C. This sudden freezing causes the formation of intra-and extracellular ice crystals, which disrupt the cell wall and alter cellular osmolality. When nerve axons are frozen, Wallerian degeneration occurs, preventing the transmission of pain signals and providing analgesia. However, the fibrous neural structures, including the perineurium and epineurium, are able to resist damage and remain intact, which facilitates axonal regeneration. The rate of this axonal regeneration is approximately 1-3 mm/day. Animal studies of cryoanalgesia have demonstrated that repair and regeneration of the axon and myelin sheath following cryoanalgesia is complete by approximately 4-6 weeks.

Cryoanalgesia has previously been used in adults for acute pain control following thoracotomy, as well as for treatment of chronic thoracic pain due to surgery or post-herpetic neuralgia. Anecdotally, cryoanalgesia has been effective at controlling acute post-operative pain in young adult and adult patients following the Nuss procedure. The procedure is particularly well-suited to the application of cryoanalgesia, as the operative exposure directly visualizes the intercostal nerves. However, no randomized trials have been performed to more rigorously evaluate this treatment. We therefore propose a randomized, prospective trial to evaluate cryoanalgesia compared to epidural analgesia for the Nuss procedure.

### 1.1 Overview of Non-Clinical Studies

Scientists have been investigating the effect of cold on the nervous system since approximately 400 BC. Since the 1970s, “cryoanalgesia” systems have been in use, which deliver

high-pressure carbon dioxide or nitrous oxide that rapidly expands, causing cooling via the Joule-Thomson effect to temperatures of -50 to -70 °C. This sudden freezing causes the formation of intra-and extracellular ice crystals, which disrupt the cell wall and alter cellular osmolality. When nerve axons are frozen, Wallerian degeneration occurs, preventing the transmission of pain signals and providing analgesia. However, the fibrous neural structures, including the perineurium and epineurium, are able to resist damage and remain intact, which facilitates axonal regeneration. The rate of this axonal regeneration is approximately 1-3 mm/day. Animal studies of cryoanalgesia have demonstrated that repair and regeneration of the axon and myelin sheath following cryoanalgesia is complete by approximately 4-6 weeks.

## 1.2 Overview of Clinical Studies

There is no published literature on cryoanalgesia in pectus excavatum repair. Studies investigating pain control following the Nuss procedure shown, with limited data, thoracic epidural analgesia to be more effective than PCA alone for the first few postoperative days. However, this method carries significant risks, including nerve damage, infection, and respiratory depression. Epidural analgesia also reduces post-operative mobility, and often necessitates the use of urinary catheters, which can increase risk of urinary tract infections. The use of epidural analgesia is limited to the first two to three post-operative days, at which time patients must be transitioned to alternate methods. This may increase length of stay, as it introduces an intermediate step prior to home oral regimen.

Cryoanalgesia has previously been used in adults for acute pain control following thoracotomy, as well as for treatment of chronic thoracic pain due to surgery or post-herpetic neuralgia. Anecdotally, cryoanalgesia has been effective at controlling acute post-operative pain in young adult and adult patients following the Nuss procedure and has led to shorter post-operative length of stay.

## 2 STUDY RATIONALE

As above, there is significant room for improvement in post-operative pain management in the Nuss procedure. The procedure is particularly well-suited to the application of cryoanalgesia, as the operative exposure directly visualizes the intercostal nerves. The majority of patients who undergo the Nuss procedure are teens and young adults. This is because patients often become symptomatic from pectus excavatum at this age. Moreover, the younger the patient, the more compliant the chest wall, allowing for effective remodeling. Because this procedure is most commonly performed in this age-group, it is important for this study to include these patients to ensure the data is applicable to the pertinent patient population.

### 2.1 Risk / Benefit Assessment

We believe that cryoanalgesia may provide better post-operative pain control following the Nuss procedure than the current standard therapy, thus allowing patients to return home sooner after surgery. This randomized study will demonstrate whether this hypothesis is valid. If so, it will provide convincing data to encourage other surgeons to adopt this new method, benefitting future patients who undergo the Nuss procedure by decreasing the significant pain associated with the procedure. Furthermore, the post-operative pain and long hospital stay are often frightening for patients considering the procedure, and knowing that the post-operative course is less arduous may make patients more comfortable prior to surgery. Shortening the post-operative hospital stay following Nuss procedure may benefit society by reducing the resources allocated to this procedure; the cost analysis included in the study will further define the possible cost savings.

Even if this study shows there is no benefit with cryoanalgesia, and, in fact, the current standard thoracic epidural analgesia is preferred, this is also important information for physicians

performing the procedure or caring for these patients post-operatively, as well as for patients themselves.

There are few additional risks to patients specifically from taking part in the study. The risks above, with the exception of the risk of randomization, are all associated either with the procedure itself, or one of the methods of pain control, both of which are being offered outside of this study. By systematically studying these two methods, we hope to provide definitive data on the preferred post-operative pain control that can inform future patient and physician decisions.

### **3 STUDY OBJECTIVES**

#### **3.1 Primary Objective**

In performing this study, we hope to determine whether cryoanalgesia can help patients recover more quickly from the Nuss procedure than standard epidural analgesia.

#### **3.2 Secondary Objectives**

We also hope to see if there is a difference in post-operative pain, medication usage, side effects, and total hospitalization cost between the two anesthetic methods.

### **4 STUDY DESIGN**

#### **4.1 Study Overview**

This study is a prospective, randomized trial to compare cryoanalgesia to standard epidural analgesia for post-operative pain management in patients undergoing minimally invasive pectus excavatum repair (the Nuss procedure). Approximately 20 subjects will be randomized in 1:1 ratio to receive cryoanalgesia or epidural analgesia at the time of their procedure. Post-operative care and analgesic protocol will be identical for all patients with the exception of continuous epidural infusion (no bolus or PCEA). Upon discharge, patients will return to clinic for 4 total follow-up appointments: 2 weeks, 1 month, 3 month, and 1 year from the date of their surgery.

Screening data will be reviewed to determine subject eligibility. Subjects who meet all inclusion criteria and none of the exclusion criteria will be entered into the study.

Total duration of subject participation will be 1 year. Total duration of the study is expected to be 1.5 years.

### **5 CRITERIA FOR EVALUATION**

#### **5.1 Primary Efficacy Endpoint**

Hospital length of stay, measured from time of surgery to time of discharge

#### **5.2 Secondary Efficacy Endpoints**

- Post-operative pain scores
- Post-operative pain medication usage
- Side effects
- Total cost of hospitalization

### **5.3 Safety Evaluations**

- Incidence of adverse events, including intractable pain, analgesic failure, infection, respiratory depression, need for further intervention, or anything else deemed by the study team to fit the description of an adverse event. Adverse events will be assessed in terms of relationship to anesthetic method, relationship to procedure, severity, subsequent treatment/intervention required, and resolution status.

## **6 SUBJECT SELECTION**

### **6.1 Study Population**

Subjects with a diagnosis of pectus excavatum, undergoing Nuss procedure who meet the inclusion and exclusion criteria will be eligible for participation in this study.

### **6.2 Inclusion Criteria**

1. Male or female  $\geq$  13 years of age at time of surgery.
2. Documentation of a pectus excavatum as evidenced by Haller index  $> 3.25$ .
3. Written informed consent (and assent when applicable) obtained from subject or subject's legal representative and ability for subject to comply with the requirements of the study.

### **6.3 Exclusion Criteria**

- Pre-op pain medication usage
- Pectus carinatum
- Poland's syndrome or other complex chest wall anomaly
- Previous repair of Pectus Excavatum by any technique
- Previous thoracic surgery
- Congenital heart disease
- Bleeding dyscrasias
- History of previous problems with anesthesia or major anesthetic risk factors
- Pregnancy or active breastfeeding
- Non-English speaker

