#### 8.3.2 Control Product

Thoracic epidural catheter will be placed by the pediatric anesthesia team prior to Nuss procedure. Catheters will be placed using sterile technique at approximately T5-6 or T6-7 interspaces; procedure specifics are dependent on the attending anesthesiologist's patient-dependent preference. Whether the patient will be awake or asleep for epidural placement will be at the discretion of the attending anesthesiologist. After placement, epidural infusion will begin with 0.1% ropivacaine and 2mcg/cc fentanyl. No bolus doses will be used.

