### **9.1.4 Physical Examination**

A complete physical examination will be performed by either the investigator or a subinvestigator who is a physician at the initial clinic visit. Qualified staff (MD, NP, RN, and PA) may complete the abbreviated physical exam at all other visits. New abnormal physical exam findings must be documented and will be followed by a physician or other qualified staff at the next scheduled visit.

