### **10.2 Visit 2- Surgery and Post-operative hospitalization**

Time of Surgery

1. Urine pregnancy test (females)
2. Open randomization allocation envelope
3. Initial analgesic application (cryoanalgesia or epidural) and Nuss procedure

According to inpatient unit protocol

1. Perform and record vital signs.
2. Perform and record oximetry.

Once per day while inpatient

1. Concomitant medications review.
2. Perform abbreviated physical examination.

Twice-per-day study visits while inpatient

1. Record any Adverse Experiences
2. Administer inpatient survey (see separate document)

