### 14.1 Data Sets Analyzed

All eligible patients who are randomized into the study and receive at least the initial analgesic application (cryoanalgesia or epidural catheter placement) and undergo Nuss procedure will be included in the analysis.

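### Eligibility screens part of epidural suitability but never states that a subject is suitable for either method, and no anesthesia-team confirmation is listed before allocation is revealed

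*Combined protocol and SAP*

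**What the plan says.** Several eligibility items bear on whether a patient can have a thoracic epidural. Section 6.3 excludes "Bleeding dyscrasias" and "History of previous problems with anesthesia or major anesthetic risk factors". Section 6.2 requires consent and "ability for subject to comply with the requirements of the study". The synopsis asks for patients who are otherwise healthy, and section 4.1 adds that "Screening data will be reviewed to determine subject eligibility". All of this comes before allocation is known and applies to both arms. Neither 6.2, 6.3 nor the synopsis names epidural or cryoanalgesia suitability as a condition of entry.

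On who assesses the patient and when, section 9.1.4 says that "A complete physical examination will be performed by either the investigator or a subinvestigator who is a physician at the initial clinic visit". Section 10.1 lists consent, history, examination, vital signs and oximetry, and ends at step 9 with the study number. On the day of surgery, section 10.2 puts one step, a urine pregnancy test, ahead of "Open randomization allocation envelope". Appendix 1 has no row for an anesthesia assessment. The pediatric anesthesia team is named only as placing the control-arm catheter (synopsis and 8.3.2).

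Section 14.1 limits the analysis to eligible randomised patients who "receive at least the initial analgesic application (cryoanalgesia or epidural catheter placement") and have the operation. Section 12.4 rules out replacing withdrawals. No section says what happens when the assigned method cannot be given, or whether patients are analysed as randomised or as treated.

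**The concern.** A patient may be fit for general anesthesia and the Nuss procedure and pass every listed criterion, yet be judged unsuitable for a thoracic catheter. If that emerges only after the envelope is opened, what follows depends on the arm. A patient allocated to cryoanalgesia is treated and analysed, and the obstacle never matters. A patient allocated to epidural does not receive the assigned application. That patient may then fall outside 14.1, or may receive the other method with no rule on which arm they count in.

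The first outcome removes control patients for a reason that does not operate in the other arm, so the groups compared on length of stay are no longer the groups that were randomised. The second keeps the patient but dilutes the contrast. With 10 patients per arm and an allowance of two dropouts in total, one or two cases are enough to notice.

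**Working it through.** **Inputs.** From section 14.5: control mean 7 days, SD 1.3, difference 2 days, alpha 0.05, power 90%, 18 patients raised to 20. From 8.1: 10 per arm. From 14.3: two-sided unpaired t test. The documents give no rate of epidural unsuitability, so every rate and count of affected patients below is an assumption.

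**1. The plan's own figure.** n per arm = 2 × [1.3 × (1.960 + 1.282) / 2]² = 8.88, rounded up to 9, so 18 in total. This reproduces the plan. For the planned t test, power from the noncentral t distribution is 86.5% at 9 per arm and 90.2% at 10 per arm.

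**2. How likely is at least one case among 10 controls?** The formula is 1 − (1 − p)^10.

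| Assumed rate p | At least one | Two or more |
|---|---|---|
| 3% | 26% | 3% |
| 5% | 40% | 9% |
| 10% | 65% | 26% |

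**3. Affected controls leave the analysis.** The noncentrality is 2 / [1.3 × √(1/10 + 1/n)], with n controls left and n + 8 degrees of freedom.
- n = 10: noncentrality 3.44, power 90.2%
- n = 9: noncentrality 3.35, power 88.4%
- n = 8: noncentrality 3.24, power 86.1%

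**4. Affected controls switch and are analysed as randomised.** Assume that each gets the full 2-day cryoanalgesia effect. With k switched of 10, the expected difference is 2 × (1 − k/10), which is 1.8 days for k = 1 and 1.6 for k = 2. The control arm also becomes a mixture, so its expected sample variance rises from 1.3² = 1.69 to 1.69 + 4 × k(10 − k)/90:
- k = 1: 1.69 + 0.40 = 2.09
- k = 2: 1.69 + 0.71 = 2.40

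A simulation of the t test with both changes (200,000 runs) gives power of about 80% for k = 1 and 67% for k = 2. Holding the SD at 1.3 would give 83.3% and 74.0%, which is too optimistic because it ignores the wider spread.

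**5. Size of a selection bias.** If the k controls who leave would have averaged s days more than the full control arm, the observed difference shifts by −k × s/(10 − k). For k = 2 and s = 1 this is −2/8 = −0.25 day, and with s = −1 it is +0.25 day. The documents give neither k nor s, nor the sign of s.

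**The case against.** Much of this is already screened. Bleeding disorders, anesthetic history, major anesthetic risk, good general health and the ability to comply all apply before allocation and to both arms. A patient who would refuse a catheter could hardly meet the compliance item in a trial that randomises to one. This stands. What remains is that the major risk factors are undefined, neither method is named, and no anesthesia assessor or time is given.

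A reader might infer from 8.3.2, where "procedure specifics are dependent on the attending anesthesiologist's patient-dependent preference", that the anesthesiologist decides after allocation whether a control patient gets a catheter. The text does not support that. The phrase sits between the level of placement and the choice of awake or asleep placement. It concerns how the catheter is placed, not whether.

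A reader might also infer that losses and switches occur only in the control arm. The documents describe no switching and report no such losses, and 14.1 would equally drop a patient in whom cryoanalgesia could not be applied. The one-sided effect holds only for obstacles specific to the epidural.

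On size, losing two controls leaves 86.1% power, close to the 86.5% that the plan's own target of 9 per arm gives with the t test. The pure loss scenario is therefore nearly inside the design. Finally, analysing every operated patient as randomised would remove the selection bias without any new criterion. That is right, but dilution from switching would remain, and only a check before allocation prevents it.

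**Conclusion.** The gap is real but narrower than a missing screen. Epidural suitability is partly covered. What is absent is a statement that the subject is suitable for either method, and a confirmation by the anesthesia team before allocation is revealed. An epidural-specific obstacle found afterwards would act on the epidural arm alone, and the plan has no rule for it.

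The loss of power is small if affected controls drop out (90.2% to 88.4% or 86.1%). It is material if they switch and are analysed as randomised (about 80% or 67%). The switching figures rest on the full 2-day effect in switched patients, and all of them rest on assumed counts of one or two. How often this would happen, and which way it would bias length of stay, cannot be derived from the documents. The stated sample size is not affected.

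**What to change.** **Eligibility.** Add to section 6.2 and the synopsis: *In the judgement of the surgeon and of the pediatric anesthesia team, under their usual hospital criteria, the subject is suitable for and willing to receive either thoracic epidural or cryoanalgesia.* Which clinical factors count is left to those teams.

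**Timing.** In section 10.1, record this judgement at Visit 1 before step 9, while allocation is concealed, and add a row to Appendix 1. The order matters. Study numbers follow enrolment order, and each is tied to one of 20 sealed envelopes (8.1). A check placed just before the envelope is opened would come after the number is assigned and could leave envelopes unused and the arms unequal. Done before step 9, a patient who fails is a screen failure and uses no number or envelope.

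**Analysis.** Add to 14.1 that anyone found unsuitable after a number is assigned stays in the assigned arm for analysis if they undergo surgery.

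**Cost.** Protocol wording and one signature from each team. The documents do not say when the anesthesia team first sees a patient, so its judgement may have to be brought forward to Visit 1. A few patients will be screened out, and the result will apply to patients suitable for both methods.
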